### **6.1.3. Dose-Limiting Toxicity Determination and Maximum Tolerated Dose Definition**

A DLT is defined as any of the events according to the NCI CTCAE version 5.0 below if both the following criteria are met:

- The event occurs during the DLT observation period of Cycle 1, between Days 1 and 21, and,
- The event is clinically significant and definitely, probably, or possibly related to abemaciclib or the combination treatment following discussion between the investigator and Lilly CRP/CRS.

Investigators, together with the Lilly CRP/CRS, can declare a DLT if a patient experiences a significant toxicity deemed to be dose-limiting.

In the event of any Grade 5 AE, enrollment will be suspended, and a thorough safety review will be performed prior to resuming enrollment.

If a patient receives <75% of any planned Cycle 1 study drug doses due to drug-related toxicity, the toxicity will be declared a DLT.

Nonhematological events:

Any Grade  $\geq 3$  nonhematological toxicity except:

- Grade 3 diarrhea that can be controlled with appropriate supportive care and lasting  $<72$  hours
- Acute diarrhea lasting  $<7$  days, secondary to irinotecan infusion, that is consistent with infusion-related cholinergic diarrhea and can be controlled with maximal supportive care
- Grade  $\geq 3$  nausea, vomiting, constipation that is manageable with maximal supportive care and lasts  $<72$  hours
- Grade 3 mucositis/stomatitis of  $<72$  hours duration
- Grade 3 fever or infection
- Grade  $\geq 3$  electrolyte abnormality that lasts  $<72$  hours, is not clinically complicated, and resolves spontaneously or responds to conventional medical interventions
- Grade  $\geq 3$  amylase or lipase that is not associated with symptoms or clinical manifestations of pancreatitis; or
- Aspartate aminotransferase/alanine transaminase elevation resolving to eligibility criteria within 7 days.

Hematological events:

- Cycle Delay: a  $>14$ -day delay in the start of a subsequent cycle because of neutropenia or thrombocytopenia in the absence of bone marrow disease progression seen on clinically indicated bone marrow biopsy (if performed).  
Note: Patients who experience dose-limiting neutropenia and/or thrombocytopenia will have these events reviewed by the sponsor to discuss attribution (bone marrow disease [baseline and subsequent, if performed and clinically indicated] versus study drugs). Patients with bone marrow disease progression will not be considered to have dose-limiting hematological toxicities.
- Grade  $\geq 3$  thrombocytopenia with clinically significant bleeding; or
- Grade  $\geq 4$  neutropenic fever.

Note: Lymphopenia is not considered a DLT unless clinically significant.

Aggregate data will be reviewed and taken into consideration for determining the RP2Ds.

The I3Y-MC-JPCS Toxicity Documentation Form must be completed and sent to Lilly for each patient during the DLT period in order for timely evaluation of DLTs.

- If a DLT is experienced during the DLT evaluation period, the I3Y-MC-JPCS Toxicity Documentation Form should be completed and sent to Lilly within 3 days of becoming aware of the DLT.
- If no DLT is experienced, the form should be completed and sent 3 days after the DLT evaluation period has ended.

## 6.2. Statistical Hypotheses

### Parts A and B

Parts A and B of Study JPCS is designed to evaluate

- the PK, safety, and tolerability of abemaciclib in combination with irinotecan and temozolomide (Part A) and abemaciclib in combination with temozolomide (Part B) in pediatric patients with relapsed/refractory solid tumors that have progressed on standard treatment
- the RP2D, and
- preliminary efficacy.

Lilly hypothesizes that abemaciclib in combination with temozolomide and irinotecan (Part A), abemaciclib in combination with temozolomide (Part B) will be sufficiently tolerable with evidence of clinical activity to support further development.

### Part C

Lilly hypothesizes that abemaciclib in combination with dinutuximab, GM-CSF, irinotecan, and temozolomide (Part C) will be sufficiently tolerable and have sufficient anti-tumor activity. The drug combination will be assessed by evaluating the PK, safety, and tolerability of the drug combination in pediatric and young adult patients with relapsed/refractory neuroblastoma.

At the same time, the anti-tumor activity is assessed using Simon's optimal 2-stage design (Simon 1989), where the null hypothesis is that ORR **CCI**, and the alternative hypothesis is that ORR **CCI**.

## 6.3. Sample Size Determination

Approximately 30 to 117 patients will be enrolled in this Phase 1b/2 study, with 24 to 60 in Parts A and B and 6 to 57 in Part C. The sample size for Parts A and B is primarily determined by DLTs (up to 6 evaluable patients at a dose level before establishing the MTD), while the sample size for Part C depends on both DLTs and responses. The maximum sample size of 57 in Part C is determined by considering dose finding and ensuring that 46 patients are treated on the RP2D. The sample size of **CCI** is determined using Simon's optimal 2-stage design with a power of 80% and a one-sided type I error rate of 0.025, given a null ORR of **CCI** against an alternative ORR of **CCI** assumed at the RP2D.

## 7. A Priori Statistical Methods

### 7.1. General Considerations

Statistical analysis of this study will be the responsibility of Lilly or its designee. The analyses for this study will be descriptive, except for possible exploratory analysis as deemed appropriate. Data analyses will be provided by study part, dose group, and for all study patients combined wherever appropriate. For continuous variables, summary statistics will include number of patients, mean, median, standard deviation, minimum, and maximum. Categorical variables will be summarized using number of patients, frequency, and percentages. Missing data will not be imputed, except for missing date of birth for analysis purpose. If birth year and month is available and date is not available or missing, date will be imputed to the 15th of that month.

The interpretation of the study results will be the responsibility of the investigator with the Lilly CRP/CRS, pharmacokineticist, and statistician. The Lilly CRP/CRS and statistician will also be responsible for the appropriate conduct of an internal review for both the final study report and any study-related material to be authorized by Lilly for publication.

Any change to the data analysis methods described in the protocol will require an amendment ONLY if it changes a principal feature of the protocol. Any other change to the data analysis methods described in the protocol, and the justification for making the change, will be described in the CSR. Additional exploratory analyses of the data will be conducted as deemed appropriate.

#### 7.1.1. Populations

For purposes of analysis, the following populations are defined in [Table JPCS.7.1](#).

**Table JPCS.7.1. Analysis Populations**

Population	Description
Entered	All participants who sign informed consent/assent
Treated Patients	Patients who have been assigned to study treatment and have received at least 1 dose of any study treatment.
Screen Failures	Patients or legal guardian (if applicable) who have signed informed consent/assent, do not meet eligibility criteria or due to AEs, physician's decision, etc. and are not enrolled.

Abbreviations: AE = adverse event; DLT = dose-limiting toxicity.

Patients who withdraw from the study before receiving study treatment will be replaced and will not be included in the safety or efficacy assessments. Safety analyses will be conducted on all patients who have been exposed to study treatment, regardless of whether they are deemed evaluable for other assessments. In Parts A, B, and Stage 1 of Part C, any patient who is discontinued from the study before completing 1 cycle will be deemed DLT non-evaluable for assessment of the combination, unless the patient experiences a DLT prior to withdrawal. If a patient is noncompliant during Cycle 1 due to reasons other than drug-related toxicity, he or she will be considered non-evaluable for assessment of the combination and may be replaced. Non-

evaluable patients may be replaced to ensure that enough patients complete 1 cycle, unless accrual to that cohort has stopped due to a DLT.

### **7.1.2. Definitions and Conventions**

Study drug refers to abemaciclib.

Study treatment refers to abemaciclib plus irinotecan and temozolomide for patients in Part A, abemaciclib plus temozolomide for patients in Part B, and abemaciclib plus dinutuximab, GM-CSF, irinotecan, and temozolomide in Part C.

Date of first dose is the date of the first dose of study drug, irinotecan, temozolomide, dinutuximab, or GM-CSF.

Study day will be calculated as the difference between the date of the event or assessment and:

- The date of first dose plus 1 for all events or assessments occurring on or after the day of first dose. For example, if an event occurs on 08 November 2020 and the date of first dose was 06 November 2020, the study day of the event is 3.
- The date of first dose for all events or assessments occurring before the day of first dose. For example, if an event occurs on 05 November 020 and the date of first dose was 06 November 2020, the study day of the event is -1.

One month is defined as 365/12 days.

Unless otherwise noted, summaries of continuous variables will include a mean, median, standard deviation, minimum, and maximum.

Unless otherwise noted, summaries of categorical variables will include the frequency and percentage (relative to the population being analyzed) of each category.

The assumptions for each statistical method will be evaluated. If there is violation of assumptions, alternative statistical methods may be used. Additional exploratory analyses of the data will be conducted as deemed appropriate. Unless otherwise stated, all tests of treatment effects will be conducted at a 1-sided alpha level of .025, and all CIs will be given at a 2-sided 95% level.

### **7.1.3. Handling of Dropouts of Missing Data**

Missing data will not be imputed, except for missing date of birth for analysis purpose. If birth year and month is available and date is not available or missing, date will be imputed to the 15th of that month.

## **7.2. Safety Analyses**

Safety analyses will be completed as specified below, unless COVID-19 impact creates a situation requiring a change to an existing analysis or a need for additional analyses as outlined by Nilsson et al. (2020).

Safety analyses will be based on the safety population, unless otherwise stated, and summarized by cohort corresponding to the actual regimen received at first dose. Additionally, all patients assigned to the RP2D (for example, the applicable cohort from dose escalation and the dose expansion cohort) within each study part may be aggregated and summarized together.

### **7.2.1. Extent of Exposure**

Drug exposure, dose intensity, and drug adjustments (dose omissions and reductions) will be summarized for abemaciclib, for temozolomide, for irinotecan, for dinutuximab, and for GM-CSF where applicable. Drug exposure will include summaries of cycles received per patient, duration on therapy, and cumulative dose. Dose intensity will be calculated as the actual cumulative amount of drug taken divided by the duration of treatment. Relative dose intensity will be calculated as

$$\frac{\text{the amount of actual drug taken}}{\text{(the amount of drug prescribed)}} \times 100\%$$

(expressed as a percentage). The summary of dose adjustments and omissions will include the reason for adjustment or omission.

Extent of exposure for abemaciclib will be measured by pill counts. Dose intensity will be expressed in mg/day. The assigned cumulative dose while on study is 2 doses per day  $\times$  planned amount of drug dose (dependent on dose level and patient BSA at the beginning of each cycle)  $\times$  number of days on treatment.

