6.1. Study Intervention(s) Administered

The investigator or his/her designee is responsible for the following:

- explaining the correct use of the drugs and planned duration of each individual's treatment to the patient/study site personnel/legal representative
- verifying that instructions are followed properly
- maintaining accurate records of study treatment dispensing and collection
- recording all concomitant medications, including premedication, on the case report form (CRF)
- at the end of the study, returning all unused medication to Lilly, or its designee, unless Lilly and sites have agreed all unused medication is to be destroyed by the site, as allowed by local law

Abemaciclib will be provided by the sponsor as 25-mg and 50-mg tablets for oral administration. Additionally, in Part C, 2.5 mg oral granules may be used. In Parts A and B, the minimum dose is 25 mg BID due to the BSA requirement of at least 0.5 m². In Part C, the minimum dose is ^{CCI} [REDACTED] or Section 10.8.

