6.4. Study Intervention Compliance

Study intervention will be administered under medical supervision by the investigator or designee. The dose of study intervention and study participant identification will be confirmed prior to the time of dosing. The date and time of each dose administered will be recorded in the source documents and will be provided to the sponsor as requested.

When participants self-administer study intervention(s) at home, compliance with study intervention will be assessed at Day 1 (± 5 days) of each Cycle starting at Cycle 2. Compliance will be assessed by direct questioning, counting returned tablets/capsules, or by weighing returned granules. Compliance assessments will be documented in the source documents and CRF. When assessing compliance of granules, refer to the "Abemaciclib Oral Granules Compliance Form". Deviation(s) from the prescribed dosage regimen should be recorded in the electronic case report form (eCRF).

A record of the quantity of self-administered study intervention(s) dispensed to and returned by each participant must be maintained and reconciled with study intervention and compliance records. Intervention start and stop dates, including dates for intervention delays and/or dose reductions, will also be recorded in the CRF.

The patient must take $\geq 75\%$ of the planned doses for study treatment in a cycle to be deemed compliant unless dose holds are necessitated by AE. As outlined in Section 6.6, dose suspensions or cycle delays may occur and will not result in a patient being considered as noncompliant. A patient may be considered noncompliant if he/she is judged by the investigator to have intentionally or repeatedly taken $\geq 125\%$ of the planned doses of study treatment in a cycle. Potential discontinuation of a patient due to study drug noncompliance will be discussed between the investigator and the Lilly CRP/CRS before any determination is made to discontinue the patient.

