#### **7.4.3. Treatment Compliance**

Treatment compliance for abemaciclib will be derived from the difference between the total number of pills dispensed and returned over the course of the patient's treatment. The number of cycles received, dose omissions, dose reductions, dose delays, and dose intensity will be summarized for all treated patients by cohort. Compliance will be assessed as the proportion of treatment that is actually taken, relative to what is expected, after accounting for protocol-defined dose adjustments. The proportion of patients who are <75% compliant with abemaciclib will be reported.

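### The SAP names only pill counts for abemaciclib exposure and compliance, although Part C allows granules and six of its ten charted doses can be given only as granules

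*SAP*

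**What the plan says.** SAP 7.2.1 (Extent of Exposure) gives one measurement method for abemaciclib: "Extent of exposure for abemaciclib will be measured by pill counts". It then says "Dose intensity will be expressed in mg/day", takes dose intensity as amount taken over duration of treatment, and takes relative dose intensity as amount taken over amount prescribed. The assigned cumulative dose is two doses a day, times the planned dose, times days on treatment.

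SAP 7.4.3 (Treatment Compliance) derives abemaciclib compliance from the "difference between the total number of pills dispensed and returned" and adds: "The proportion of patients who are <75% compliant with abemaciclib will be reported". Neither section mentions granules.

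The protocol describes two formulations. Section 6.1 says "Abemaciclib will be provided by the sponsor as 25-mg and 50-mg tablets for oral administration" and then "Additionally, in Part C, 2.5 mg oral granules may be used". It does not allow the two to be mixed within one dose. Section 6.4 lists direct questioning, "counting returned tablets/capsules, or by weighing returned granules" as the ways to assess compliance, names a separate compliance form for granules, and sends the results to source documents and the CRF.

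The granule text in Protocol 6.4 came in with Amendment (e), according to Protocol Appendix 11. SAP version 2 says that it was revised for consistency with Amendment (e) and to add the Part C analyses (SAP Section 4), and it lists granule acceptability among its objectives (SAP Section 5).

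**The concern.** The SAP's only stated source for abemaciclib exposure does not exist for a patient who takes granules. For a patient on granules throughout, pills dispensed and pills returned are both zero. For a patient who changes formulation, a pill count sees only the tablet period, while the denominator runs over all days on treatment.

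The summaries at stake are cumulative dose, dose intensity, relative dose intensity and the proportion below 75% compliance in Part C. The error would not fall at random. It would concentrate in the smallest children and in those reduced to low doses for toxicity, the patients for whom a reader most wants to know how much drug was delivered.

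**Working it through.** **Inputs.** Tablet strengths 25 and 50 mg and granule strength 2.5 mg (Protocol 6.1); Part C dosing chart and granule chart (Protocol Appendix 8); Part C reduction table (Protocol 6.6); 21-day cycle, twice-daily dosing.

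**1. Reproduce the plan's granule chart.** Granules per dose = dose / 2.5 mg, which should also equal device setting × number of dispensings. Examples: 10 / 2.5 = 4 and 4 × 1 = 4; 22.5 / 2.5 = 9 and 9 × 1 = 9; 75 / 2.5 = 30 and 15 × 2 = 30; 100 / 2.5 = 40 and 20 × 2 = 40. All ten rows agree, so the chart is internally sound.

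**2. Which doses can be made from tablets?** A dose is feasible if it equals 25a + 50b mg for whole numbers a and b.
- Feasible: 25, 50, 75, 100 mg (4 of 10).
- Not feasible: 10, 12.5, 15, 17.5, 20, 22.5 mg (6 of 10).

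This assumes that part-tablets are not given. Protocol 6.1 has abemaciclib swallowed whole, and 6.1.2 describes dispersing tablets but does not mention giving a fraction of one. The Parts A and B reduction table stops at 25 mg, which fits a tablet floor.

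**3. Who reaches a granule-only dose?**

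| Route | 55 mg/m² | 30 mg/m² |
|---|---|---|
| Starting dose below 25 mg | BSA 0.20–0.43 m² | BSA 0.30–0.79 m² |
| Start 25 mg, first reduction to 17.5 mg, second to 10 mg | BSA 0.44–0.68 m² | BSA 0.80–1.24 m² |
| Start 50 mg, second reduction to 17.5 mg | BSA 0.69–1.13 m² | BSA 1.25–2.08 m² |

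Granules are also charted for 25 to 100 mg, and after the Cycle 3 Day 1 PK sample patients may change formulation for other reasons (Protocol 6.1). The gap can therefore reach patients who could have used tablets.

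**4. Granule-only patient, 22.5 mg twice daily, one full cycle taken.** Planned amount = 2 × 22.5 × 21 = 945 mg (378 granules); planned dose intensity = 945 / 21 = 45 mg/day; 75% line = 0.75 × 945 = 708.75 mg. A pill count gives 0 pills taken out of 0 dispensed, so compliance is 0/0 and dose intensity is either 0 mg/day or missing.

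**5. Patient who changes formulation (hypothetical, every dose taken).** Three cycles at 25 mg twice daily as tablets: 2 × 25 × 63 = 3,150 mg. Then a reduction to 17.5 mg twice daily as granules for three cycles: 2 × 17.5 × 63 = 2,205 mg. The expected total after the reduction is 3,150 + 2,205 = 5,355 mg.
- All formulations counted: 5,355 / 5,355 = 100%.
- Tablets only: 3,150 / 5,355 = 58.8%, so a fully adherent patient is reported below 75%.

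**6. Is the gap only one of vocabulary?** Reading pill to include a granule does not close it. The protocol weighs returned granules rather than counting them, and the SAP has no rule for turning weight into mg. The mass of one granule is not in the documents.

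**The case against.** The strongest reply is that this concerns a data source, not a definition. The SAP's quantities are formulation-neutral: amount taken per day in mg, amount taken over amount prescribed, proportion taken relative to expected. Protocol 6.4 already requires returned granules to be weighed, a dedicated form, CRF entry of compliance assessments, recording of dosing deviations, and a record of quantities dispensed and returned. A sensible analyst would use those data. This stands, and it means that a reader who concludes that the figures cannot be computed at all goes too far. The appeal to the SAP's no-imputation rule also fails, because data that are planned and collected are not missing. What remains is that the SAP's written rule, followed literally, gives the wrong answer, and nothing in it directs the programmer to the granule data.

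A reader might also infer that the RP2D is at risk. The documents do not support that. Part C confirms the MTD as RP2D if Rules A (DLTs), B (discontinuations for treatment-related AEs) and C (responders) are not triggered (Protocol 4.1.2, SAP 7.7.2), and none uses exposure or the 75% compliance figure. Protocol 4.1.3 adds a general review of aggregate data but names no exposure measure. The Cycle 1 threshold of 75% of planned doses for DLT evaluability (Protocol 4.1.1, 4.1.3 and 9.3) is a separate rule that is not tied to SAP pill counts. SAP 7.1.1 does mention Cycle 1 noncompliance, but without reference to SAP 7.4.3.

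Six of ten is a count of chart rows, not of patients. The 0.43 m² limit at 55 mg/m² is low, and the 0.79 m² limit applies only if 30 mg/m² is used. The number affected could be small. Some Protocol 6.1 text next to the formulation rules is redacted and might narrow it further.

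**Conclusion.** The mismatch is real and minor. SAP 7.2.1 and 7.4.3 specify a tablet-only method for a part of the trial that allows granules and, at six of ten charted doses, can use nothing else. As written, the abemaciclib exposure and compliance summaries would be undefined for patients on granules throughout and understated for those who change formulation (58.8% instead of 100% in the worked example).

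The effect stops at descriptive tables; ORR and its analysis, the Simon design and the sample size do not use these quantities either. The number of patients affected cannot be calculated, because the documents give no BSA distribution or expected granule use.

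The conclusion rests on two assumptions: that tablets are given whole, and that the SAP is applied literally. If the programmer goes to the Protocol 6.4 granule data on their own initiative, the tables can be right, but by a method that the SAP does not specify.

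**What to change.** In SAP 7.2.1 and 7.4.3, replace the pill-count sentences with one definition of abemaciclib taken, in mg:

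- tablets: (number dispensed − number returned) × tablet strength;
- granules: (weight dispensed − weight returned) × a stated mg-per-weight factor, cited from the granule compliance form named in Protocol 6.4 or from another identified source;
- total: the sum over both formulations and all periods on treatment.

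Use that total for cumulative dose, dose intensity, relative dose intensity and the proportion below 75%, with the expected amount taken over the same periods and after protocol-defined dose adjustments.

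The cost is a few SAP sentences and the programming behind them. No new visit or procedure appears to be needed, since Protocol 6.4 already requires quantities dispensed and returned to be recorded and returned granules to be weighed. Two points need confirming first: the conversion factor, and that the form captures the dispensed as well as the returned weight. The form's content is not in the documents.
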